4. ANALYSIS SETS (POPULATIONS FOR ANALYSIS)

Data for all participants will be assessed to determine if participants meet the criteria for inclusion in each analysis population prior to unblinding and releasing the database and classifications will be documented per standard operating procedures.

Population	Description
Full Analysis Set (FAS)	All participants randomly assigned to study intervention regardless of whether or not study intervention was administered.
Safety Analysis Set (SAS)	All participants who receive at least 1 dose of study intervention. Participants will be analyzed according to the intervention they actually received. A randomized but not treated participant will be excluded from the safety analyses.

Population	Description
Modified Intent -To Treat (mITT)	All participants randomly assigned to study intervention who take at least 1 dose of study intervention and with at least 1 postbaseline visit through Day 28 who were treated ≤ 3 days after COVID symptoms onset. Participants will be analyzed according to the study intervention to which they were randomized.
Modified Intent-To-Treat (mITT1)	All participants randomly assigned to study intervention, who take at least 1 dose of study intervention. Participants will be analyzed according to the study intervention they were randomized.
Per-Protocol (PP)	All participants in the mITT1 set without important protocol deviations considered to impact the interpretation of the primary efficacy endpoint. Protocol deviations will be reviewed to generate the list of participants with significant deviations to be excluded from the PP analysis set. The PP exclusion criteria will be finalized prior to breaking the blind.

Both the mITT1 and PP analysis sets will be used in the analyses of the primary efficacy endpoint, with the mITT1 being primary. For proportion of COVID-19 related hospitalization or death from any cause and all other efficacy endpoints, mITT1 will be used. The Safety Analysis Set will be used in the analyses of the safety data.

Multiple Enrollers:

If a participant enters/is randomized into Study C4671002 more than once or is enrolled in Study C4671002 and in 1 or 2 other Phase 2/3 nirmatrelvir/ritonavir studies:

- (1) The primary and key secondary efficacy analyses will be performed by considering all enrolled participants (subject IDs) as independent participants.

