6. ANALYSES AND SUMMARIES

6.1. Primary Endpoint

6.1.1. Primary Endpoint/Estimand Analysis

6.1.1.1. Main Analysis

The primary endpoint is time (days) to sustained alleviation of all targeted COVID-19 signs/symptoms through Day 28 in the mITT1 population.

Sustained alleviation of all targeted COVID-19 signs/symptoms is defined as the event occurring on the first of 4 consecutive days when all symptoms scored as moderate or severe at study entry are scored as mild or absent AND all symptoms scored mild or absent at study entry are scored as absent. The first day of the 4 consecutive-day period will be considered the First Event Date.

For symptoms with no reported severity in baseline, the symptom will have to be absent in order to be counted as sustained alleviated/resolved (missing severity at baseline will be treated as mild).

Day 25 is the last possible day the symptom alleviation and resolution endpoints can be achieved (definition includes data from the subsequent three days) and Day 28 is the last day participants report their daily signs and symptoms.

The time to sustained symptom alleviation/resolution for the purpose of this study is defined as:

- For a participant with sustained symptom alleviation/resolution (event), time to event will be calculated as (First Event Date) – (First Dose Date) +1.

- For a participant that either completes Day 28 of the study or discontinues from the study before Day 28 without sustained symptom alleviation/resolution (censored), censoring date will be at the last date on which symptom alleviation/resolution is assessed, and time will be calculated as (Censoring Date) – (First Dose Date) +1 or Day 25 whichever occurs first.

The decision to require 4 consecutive days of all targeted symptoms alleviation/resolution was based on exploratory analyses of data from the ACTIV-2/A5401 study, which suggested that this choice (rather than requiring fewer consecutive days) better captured sustained symptom resolution with low probability of subsequent relapse.

Participants who are hospitalized for the treatment of COVID-19 or death from any cause during the 28-day period will be classified as not achieving sustained symptom alleviation and will be censored at Day 25.

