6.1.1.2. Sensitivity and Supplemental Analyses

Sensitivity analyses will be performed to the primary efficacy endpoint:

The primary efficacy analyses will also be conducted using the PP population as supplemental analyses.

The primary endpoint will also be analyzed in which participants who discontinued the study before Day 28 without event will be censored at Day 25.

For sensitivity analysis of primary endpoint, Cox proportion hazard models with terms including treatment and treatment strata (ie, region, vaccination, baseline serology, baseline viral load $<10^4$ copies/mL vs $\geq 10^4$ copies/mL). These factors will be used to estimate the hazard ratio (the ratio of alleviation of all targeted signs and symptoms) and its 95% CI. Additional analyses may be performed adjusting for baseline covariates (such as age, gender, etc) as additive terms to the primary model, if necessary.

Based on FDA request, a sensitivity analysis excluding participants only from Site 1488 will be conducted as well.

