6.2.2. Incidence of SAEs and AEs Leading to Discontinuations

The incidence of SAEs and AEs leading to discontinuation will be summarized by treatment group using the SAS population.

6.2.3. Proportion of Participants with COVID-19 Related Hospitalization or Death From Any Cause Through Day 28

The estimand for proportion of participants experiencing COVID-19 related hospitalization or death from any cause through Day 28 is the difference in proportions of participants experiencing COVID-19 related hospitalization or death from any cause through Day 28 in nonhospitalized adult patients with COVID-19 who are at low risk of progression to severe disease and were treated ≤ 5 days after COVID-19 symptom onset. This will be estimated irrespective of adherence to randomized treatment.

The statistical methodology for proportion of participants with COVID-19 related hospitalization or death from any cause through Day 28 will be as follows:

The cumulative proportion of participants hospitalized for the treatment of COVID-19 or death during the first 28 days of the study will be estimated for each treatment group using the Kaplan-Meier method to take account of lost to follow-up and summarized graphically for each treatment group. The estimand is the difference of the proportions in the 2 groups and its 95% CI will be presented, as well as, the associated two sample proportion test (Wald test results). For the 95% CI, the corresponding estimate of the standard error is computed using Greenwood's formula⁴. The Greenwood's formula to estimate the variance of the difference of proportions at Day 28 is $[\text{Var}(S_{PF}(28)) + \text{Var}(S_{\text{Placebo}}(28))]$. Instead of dealing with $S(t_i)$ the log-log approach to CI will be used. The 95% CI will be computed for the estimate of $L(t) = \log(-\log(S(t)))$, the log hazard function.

The CI will be in the right range when transformed back to $S(t) = \exp(-\exp(L(t)))$. Antilogging this CI will give a 95% confidence interval for the difference itself.

A sensitivity analysis for proportion of participants with COVID-19 related hospitalization or death from any cause through Day 28 will be provided using mITT1 as follows:

For participants with missing data due to lost to follow up for COVID-19 related hospitalization or death from any cause, the sensitivity analysis will implement the following event imputation methodology for those with missing data:

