- If the participant's last observed data is prior to Day 21, then impute as an event with event day as day of last observed data +1.
- If the participant's last observed data is on or after Day 21, then no imputation for event will be done and participant remains censored at day of last observed data.

6.2.4. Proportion of Participants with Death (all cause) through Week 24

Descriptive statistics will be used to summarize proportion of death through Week 24 by treatment group using mITT1 populations. Treatment comparisons between groups will be presented as odds ratios with 95% confidence intervals and P-value based on logistic regression model (if data permit).

If zero counts are observed in either treatment group, the Fishers Exact test will be performed (instead of logistic regression) and p-value provided.

The participants enrolled under or after protocol amendment 6 will not include this summary.

6.2.5. Number of COVID-19 Related Medical Visits through Day 28

The number of COVID-19 related medical visits will be analyzed with a negative binomial regression model, using the log total number of days of data collection as the participant offset variable (if data permit). The resulting analysis will evaluate the difference in estimated rate of number of medical visits between treatment groups and the associated 95% CI. The analyses will be done using mITT1 populations.

6.2.6. Number of Days of Hospital and ICU Stay in Participants with COVID-19 Related Hospitalization

Health resource utilization data will be summarized by treatment group for each treatment. The analyses will be done using mITT1 populations. Descriptive statistics (ie, mean, median, range) will be used to summarize this endpoint.

The resulting analysis will provide the estimated difference in the average of number of days stayed in the hospital between treatment groups, with p-value and 95% confidence interval. The analyses will be done using the mITT1 population.

6.2.7. Proportion of Participants with Severe Signs/symptoms Attributed to COVID19 through Day 28

Participants will record a daily severity rating of their symptom severity over the past 24 hours based on a 4-point scale in which 0 is reported if no symptoms were present; 1 if mild; 2 if moderate; and 3 if severe. A participant with severe score for any targeted symptoms post-baseline will be counted as severe.

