9. APPENDICES

Appendix 1. Summary of Efficacy Analyses

Endpoint	Analysis Type	Population	Data Inclusion and Rules for Handling Intercurrent Events and Missing Data	Analysis Model
Time (days) to sustained alleviation of all targeted COVID-19 signs/symptoms through Day 28.	Primary efficacy Analysis	mITT1	All data collected will be included. Missing severity at baseline will be treated as mild. Other missing data will be estimated with KM (lifetest) procedure	Kaplan-Meier & Log rank test
Time (days) to sustained alleviation of all targeted COVID-19 signs/symptoms through Day 28.	Sensitivity analysis for primary endpoint	mITT1	All data collected will be included. Missing severity at baseline will be treated as mild.	Cox proportional hazard model
Time (days) to sustained alleviation of all targeted COVID-19 signs/symptoms through Day 28.	Sensitivity analysis for primary endpoint	mITT1 exclude site 1488	All data collected will be included. Missing severity at baseline will be treated as mild.	Cox proportional hazard model
Time (days) to sustained alleviation of all targeted COVID-19 signs/symptoms through Day 28.	Supplemental analysis for primary endpoint	PP	Participants who discontinued the study before Day 28 without event will be censored at Day 25.	Kaplan-Meier & Log rank test
Time (days) to sustained alleviation of all targeted COVID-19 signs/symptoms through Day 28.	Sensitivity analysis for Primary Efficacy analysis for multiple enrollers	mITT1 including only data with first randomization within the study	All data collected will be included regardless of intercurrent events. Kaplan-Meier method to take account of losses to follow-up.	Kaplan-Meier method
Time (days) to sustained alleviation of all targeted COVID-19 signs/symptoms through Day 28 by vaccination status	Subgroup analysis for primary endpoint	mITT1	Use baseline variables as described in Section 6.4.	Cox proportional hazard model
Proportion of participants with COVID-19 related hospitalization or death from any cause through Day 28	Key secondary analysis	mITT1	All data collected will be included regardless of intercurrent events. Kaplan-Meier method to take account of losses to follow-up.	Kaplan-Meier method

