Proportion of participants with COVID-19 related hospitalization or death from any cause through Day 28	Sensitivity analysis for key secondary endpoint	mITT1	If the participant's last observed data is prior to Day 21, then impute as an event with event day as day of last observed data +1. If the participant's last observed data is on or after Day 21, do not impute an event and	Kaplan-Meier method

Endpoint	Analysis Type	Population	Data Inclusion and Rules for Handling Intercurrent Events and Missing Data	Analysis Model
			participant remains censored at day of last observed data.	
Proportion of participants with COVID-19 related hospitalization or death from any cause through Day 28	Sensitivity analysis for key secondary efficacy analysis for multiple enrollers	mITT1 including only data with first randomization within the study	All data collected will be included regardless of intercurrent events. Kaplan-Meier method to take account of losses to follow-up.	Kaplan-Meier method
Proportion of participants with COVID-19 related hospitalization or death from any cause through Day 28 by vaccination status	Subgroup analysis for key secondary endpoint	mITT1	Subset analysis identified in Section 6.4.	Kaplan-Meier method
Proportion of participants with COVID-19 related hospitalization or death from any cause through Day 28	Supplemental analysis for key secondary efficacy endpoint	PP	Participants who discontinued the study before Day 28 without event will be censored at Day 25.	Kaplan-Meier & Log rank test
Proportion of participants with death (all cause) through Week 24.	Secondary analysis	mITT1	All data collected will be included regardless of intercurrent events exclude participants enrolled under PA6	Logistic Regression
Number of COVID-19 related medical visits through Day 28.	Secondary analysis	mITT1	All data collected will be included regardless of intercurrent events. Missing data will not be imputed.	Descriptive statistics (based on negative Binomial Model)
Number of days in hospital and ICU stay in participants with COVID-19 related hospitalization through Day 28.	Secondary analysis	mITT1	All data collected will be included regardless of intercurrent events. Missing data will not be imputed.	Descriptive statistics
Proportion of participants with severe signs/symptoms attributed to COVID-19 through Day 28.	Secondary Efficacy Analysis	mITT1	All data collected will be included regardless of intercurrent events, LOCF for missing data.	Logistic regression model

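### The per-protocol analysis of hospitalisation or death in SAP Appendix 1 uses the symptom endpoint's Day 25 censoring rule, so early leavers count as event-free on days nobody observed (minor; this supplemental analysis only)

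*SAP*

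**What the plan says.** The PP row for hospitalisation or death in SAP Appendix 1 is labelled supplemental, names Kaplan-Meier and the log-rank test, and gives one data rule: "Participants who discontinued the study before Day 28 without event will be censored at Day 25". The PP row for the primary symptom endpoint, earlier in the same table, carries the same sentence.

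The reason for Day 25 is in SAP 6.1.1.1: "Day 25 is the last possible day the symptom alleviation and resolution endpoints can be achieved", because four consecutive diary days must fit by Day 28. SAP 6.1.1.2 attaches the rule to that endpoint: "The primary endpoint will also be analyzed in which participants who discontinued the study before Day 28 without event will be censored at Day 25". Protocol 9.3.2.1 says the same.

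For hospitalisation or death, SAP 6.2.3 uses a 28-day window. The Appendix 1 entry for the main mITT1 analysis relies on the "Kaplan-Meier method to take account of losses to follow-up". The sensitivity analysis in 6.2.3 has a two-part rule for participants lost to follow-up. For early loss: "If the participant's last observed data is prior to Day 21, then impute as an event with event day as day of last observed data" plus one. For last data on or after Day 21, the "participant remains censored at day of last observed data".

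SAP Section 4 names PP for the primary endpoint and then states: "For proportion of COVID-19 related hospitalization or death from any cause and all other efficacy endpoints, mITT1 will be used". Section 6.2.3 describes no PP analysis.

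**The concern.** A hospitalisation or death can occur on any day through Day 28, so Day 25 has no special meaning for this endpoint. A participant last seen on Day 3 would stay in the risk set for 22 further days (25 − 3) in which a hospitalisation would generally go unrecorded.

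The rule also changes direction when it moves between endpoints. For symptoms, holding a leaver at risk to Day 25 treats that person as not recovered, which is the unfavourable outcome. For hospitalisation or death, it treats the same person as free of the unfavourable outcome.

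This is the only PP analysis listed for the endpoint that led to the larger sample size. A PP check should differ from the main analysis only through the choice of participants. As written, it also differs through follow-up time that was never observed.

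**Working it through.** **Inputs from the documents**
- SAP 2.3: 1880 participants before dropout, 26 events, 70% reduction, 5% discontinuation; the initial calculation used 18% discontinuation.
- SAP 2.2: 1:1 allocation, so 940 per arm.
- Protocol 2.2.2: first-interim rates 8/329 = 2.4% and 2/333 = 0.6%.

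**Plan's own figure.** 1880 / (1 − 0.05) = 1979, against a stated 1980. It is reproduced. The disputed row states no figure of its own.

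**Assumptions.** Constant daily hazard over 28 days; leaving unrelated to risk; whole-trial dropout applied to the PP set; all leavers go on one day L before Day 25.

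**Implied risks.** If placebo risk is p and active risk 0.3p, then 940 × 1.3p = 26. So p = 26 / (940 × 1.3) = 2.13% and 0.3p = 0.64%. The true difference is −1.49 points.

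**Effect of the rule.** Let a fraction d leave on day L. On days L+1 to 25, events arise only among the fraction 1 − d still observed, but the denominator includes everyone, so the estimated hazard is multiplied by 1 − d. Days 26 to 28 are unaffected. For rare events, estimated incidence is therefore

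true incidence × [1 − d × (25 − L) / 28].

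With equal dropout the difference shrinks by the same factor. A day-by-day expected Kaplan-Meier calculation gives the same figures:

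| Dropout (both arms) | Leaving day | Shrinkage d(25 − L)/28 | Difference (true −1.49) |
|---|---|---|---|
| 5% (plan) | 3 | 0.05 × 22/28 = 3.9% | −1.43 |
| 5% (plan) | 10 | 0.05 × 15/28 = 2.7% | −1.45 |
| 5% (plan) | 20 | 0.05 × 5/28 = 0.9% | −1.48 |
| 10% (assumed) | 3 | 0.10 × 22/28 = 7.9% | −1.37 |
| 18% (initial calculation) | 3 | 0.18 × 22/28 = 14.1% | −1.28 |

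**Unequal dropout on Day 3 (assumed rates)**
- 8% placebo, 2% active: 2.128 × (1 − 0.08 × 22/28) = 1.994; 0.638 × (1 − 0.02 × 22/28) = 0.628. The difference is −1.37, about 8% too small.
- 2% placebo, 8% active: 2.095 and 0.598. The difference is −1.496, about 0.5% too large, although both incidences are understated.

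**Second set of risks.** With 2.4% and 0.6%, 990 per arm, leaving spread over Days 1 to 27 or confined to Days 1 to 7, and a constant or front-loaded hazard, the true −1.80 points becomes −1.73 to −1.78 at 5% dropout and −1.56 to −1.71 at 18%.

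**Inference.** At 5% dropout on Day 3, the standard error of the difference falls from 0.550 to 0.529 points. Estimate over standard error is 1.489/0.550 = 2.71 under last-day censoring and 1.431/0.529 = 2.71 under the Day 25 rule. The risk ratio stays at 0.30. The at-risk split between arms is essentially unchanged, so the log-rank test hardly moves.

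**Late leavers.** For someone leaving on Day 26 or 27 the rule moves censoring back to Day 25 and discards one or two observed days.

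**The case against.** The strongest reply is that nothing rests on this cell. The row is supplemental, Section 4 assigns the endpoint to mITT1, and all further p-values are nominal. The sensitivity analysis in 6.2.3 already tests early loss in the opposite direction, by imputing events. At the planned dropout the shift is 0.06 points at most, against a standard error of about 0.55. All of this stands, and it sets the severity at minor. It does not make the rule right for this endpoint.

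Several stronger readings are tempting, and the documents do not support them:
- **That the main result for hospitalisation or death is biased.** The mITT1 main, lost-to-follow-up and multiple-enroller rows do not use Day 25.
- **That 6.2.3 censors every leaver at the last observed day.** That wording covers only last data on or after Day 21, in the sensitivity analysis. A Day 3 leaver lost to follow-up would be imputed there as an event. Last-day censoring in the main analysis is a fair inference from its use of Kaplan-Meier for losses, but it is not spelled out.
- **That the effect is attenuated by 4 to 8%, fixed by dropout alone.** The upper end needs departures as early as Day 3 together with 10% or unequal dropout. Leaving time and hazard shape matter too.
- **That nothing is learned after a participant leaves.** The early-termination visit includes a vital status check, and Protocol 7.2.1 allows public records to be used for vital status where local law permits. Participants who only stop study drug remain in follow-up. The gap is mainly in hospitalisation after withdrawal from the study.

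The number of early leavers who will remain in the PP set is also unknown, because its exclusion criteria are to be settled before unblinding.

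**Conclusion.** The concern holds in limited form. The Day 25 rule is unsuited to this endpoint: it understates incidence in each arm for participants leaving before Day 25 and drops observed days for those leaving on Days 26 and 27. Under a constant hazard and leaving unrelated to risk, equal 5% dropout attenuates the difference by about 1 to 4%; 18% leaving on Day 3 would attenuate it by about 14%. Unequal dropout can make the distortion larger, or nearly cancel it in the difference. Leaving that is related to risk was not modelled and could make the bias larger.

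Only the supplemental PP analysis is affected, so the severity is minor. That the sentence was carried over from the symptom row is likely, given the identical wording and the absence of this analysis from the body text, but it is an inference.

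**What to change.** In the PP row for hospitalisation or death in SAP Appendix 1, replace the Day 25 sentence with: *participants without an event are censored at the last date of observed data or Day 28, whichever is earlier*. This is in line with the main mITT1 Kaplan-Meier analysis, which takes account of loss to follow-up.

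Then make the SAP consistent: either add the PP analysis of this endpoint to Sections 4 and 6.2.3, or delete the row. The Day 25 rule can stay in the symptom-endpoint row.

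The cost is one table cell and, if the analysis is kept, a sentence in each of two sections. No new data are needed and no sample size changes.

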Appendix 2. Data Derivation Details

Appendix 2.1. Definition and Use of Visit Windows in Reporting

The following table defines the visit windows and labels to be used for reporting:

Visit Number	Visit Label	Definition [Day window]
2	Baseline	= Day -2 to Day 1
3	Day 3	= Day 3, with a window of ± 1 Day, (ie, Days 2 to 4)
4	Day 5	= Day 5, with a window of ± 1 Day, (ie, Days 4 to 6)
5	Day 10	= Day 10, with a window from Days 7 to 11
6	Day 14	= Day 14, with a window from Days 12 to 17
7	Day 21	= Day 21, with a window from 18 to 24
8	Day 34	= Day 34, with a window from days 25 to 37
9	Week 12	= Day 84, with a window of ± 7 Days, (ie, Days 77 to 91)
10	Week 24	= day 168 with a window of ± 7 days, (ie, Days 161 to 175)

- Viral Load: Baseline visit is set up according to study days of Day -2 to Day 1. The only viral load results collected after the start of dosing during the Baseline visit that are treated as Baseline data are those that were collected within 1 hour post start of dosing.
- Labs, COVID-19 Signs and Symptoms, Vital Signs: Baseline window will be Day -2 to Day 1, without any consideration to the time factor.
- When data from study Day 4 has an overlap between Day 3 and Day 5 windows, decision made is to assign the window according to the nominal visit. The rule will not be applicable to other study days 2 and 3 for Day 3 window, and days 5 and 6 for Day 5 window.
- If multiple readings fall into the same window, choose the one closer to the target day. If equidistant, then select the later one after the target day. If multiple observations fall on the same day after the windowing logic has been applied, average observations.

